5.2 Exclusion Criteria

Subjects are excluded from the study if any of the following criteria apply:

Disease Related

- 201 Severe renal dysfunction, defined as an estimated glomerular filtration rate (eGFR) < 30 mL/min/1.73 m² during screening
- 202 History or clinical evidence of active liver disease or hepatic dysfunction, defined as aspartate aminotransferase (AST) or alanine aminotransferase (ALT) > 3 x upper limit of normal (ULN), or total bilirubin (TBL) > 2 x ULN during screening
- 203 Inherited or other bleeding disorders
- 204 Recent major cardiovascular event (myocardial infarction, unstable angina, PCI, CABG, or stroke) within 6 months prior to day 1
- 205 Planned cardiac surgery, PCI or carotid stenting, or planned major non-cardiac surgery during the study period

Other Medical Conditions

- 206 Malignancy (except non-melanoma skin cancers, cervical in-situ carcinoma, breast ductal carcinoma in situ, or stage 1 prostate carcinoma) within the last 5 years prior to day 1
- 207 Moderate to severe heart failure (New York Heart Association (NYHA) Functional Classification III or IV at day 1) or last known left ventricular ejection fraction $< 30\%$
- 208 Uncontrolled cardiac arrhythmia defined as recurrent and highly symptomatic ventricular tachycardia, atrial fibrillation with rapid ventricular response, or supraventricular tachycardia that are not controlled by medications, in the past 3 months prior to day 1
- 209 Uncontrolled hypertension at day 1, defined as an average systolic blood pressure of ≥ 160 mmHg or an average diastolic blood pressure of ≥ 100 mmHg at rest
- 210 Fasting triglycerides ≥ 400 mg/dL (4.5 mmol/L) during screening

- 211 Type 1 diabetes or poorly controlled ($\text{HbA1c} \geq 8.5\%$) type 2 diabetes mellitus as determined by central laboratory at screening
- 212 Known active infection or major hematologic, renal, metabolic, gastrointestinal or endocrine dysfunction, or a chronic disease or infection (eg, HIV) that is not currently stable and appropriately managed in the judgment of the investigator at day 1

Prior/Concomitant Therapy

- 213 Previously received treatment with antisense oligonucleotides (ASO), siRNA therapies (eg, inclisiran), or any experimental therapy targeting Lp(a)
- 215 Currently undergoing lipid apheresis or < 3 months since last apheresis treatment at day 1

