- Wilson's disease and hemochromatosis
- Nonalcoholic fatty liver disease including steatohepatitis
- Non-hepatic causes (eg, rhabdomyolysis, hemolysis)

If investigational product(s) is/are withheld, the subject is to be followed for possible drug induced liver injury (DILI) according to recommendations in the last section of this appendix.

Rechallenge may be considered if an alternative cause for impaired liver tests (ALT, AST, ALP) and/or elevated TBL, is discovered and the laboratory abnormalities resolve to normal or baseline (see next section in this appendix).

Table 11-2. Conditions for Withholding and/or Permanent Discontinuation of Amgen Investigational Product and Other Protocol-required Therapies Due to Potential Hepatotoxicity

Analyte	Temporary Withholding	Permanent Discontinuation
TBL	> 3x ULN at any time	> 2x ULN
INR	--	> 1.5x (for subjects not on anticoagulation therapy)
AST/ALT	> 8x ULN at any time > 5x ULN but < 8x ULN for ≥ 2 weeks > 5x ULN but < 8x ULN and unable to adhere to enhanced monitoring schedule > 3x ULN with clinical signs or symptoms that are consistent with hepatitis (such as right upper quadrant pain/tenderness, fever, nausea, vomiting, and jaundice)	OR AND In the presence of no important alternative causes for elevated AST/ALT and/or TBL values > 3x ULN (when baseline was < ULN)
ALP	> 8x ULN at any time	--

ALP = alkaline phosphatase; ALT = alanine aminotransferase; AST = aspartate aminotransferase; INR = international normalized ratio; TBL = total bilirubin; ULN = upper limit of normal

Criteria for Rechallenge of Amgen Investigational Product and Other Protocol-required Therapies After Potential Hepatotoxicity

The decision to rechallenge the subject is to be discussed and agreed upon unanimously by the subject, investigator, and Amgen.

If signs or symptoms recur with rechallenge, then olpasiran is to be permanently discontinued. Subjects who clearly meet the criteria for permanent discontinuation (as described in [Table 11-2](#)) are never to be rechallenged.

Drug-induced Liver Injury Reporting and Additional Assessments

Reporting

To facilitate appropriate monitoring for signals of DILI, cases of concurrent AST or ALT and TBL and/or INR elevation, according to the criteria specified in the above, require the following:

- The event is to be reported to Amgen as a serious adverse event within 24 hours of discovery or notification of the event (ie, before additional etiologic investigations have been concluded)

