- The appropriate Case Report Form (CRF) (eg, Events CRF) that captures information necessary to facilitate the evaluation of treatment-emergent liver abnormalities is to be completed and sent to Amgen

Other events of hepatotoxicity and potential DILI are to be reported as serious adverse events if they meet the criteria for a serious adverse event defined in Section 11.4.

Additional Clinical Assessments and Observation

All subjects in whom investigational product(s) or protocol-required therapies is/are withheld (either permanently or conditionally) due to potential DILI as specified in Table 11-2 or who experience AST or ALT elevations > 3 x upper limit of normal (ULN) or 2-fold increases above baseline values for subjects with elevated values before drug are to undergo a period of “close observation” until abnormalities return to normal or to the subject’s baseline levels. Local laboratory results are required in the event that additional tests are needed for DILI criteria.

Assessments that are to be performed during this period include:

- Repeat AST, ALT, ALP, bilirubin (BIL) (total and direct), and INR within 24 hours
- In cases of TBL > 2 x ULN or INR > 1.5 , retesting of liver tests, BIL (total and direct), and INR is to be performed every 24 hours until laboratory abnormalities improve

Testing frequency of the above laboratory tests may decrease if the abnormalities stabilize or the investigational product(s) or protocol-required therapies has/have been discontinued AND the subject is asymptomatic.

Initiate investigation of alternative causes for elevated AST or ALT and/or elevated TBL.

The following are to be considered depending on the clinical situation:

- Complete blood count with differential to assess for eosinophilia
- Serum total immunoglobulin (Ig)G, anti-nuclear antibody anti-smooth muscle antibody, and liver kidney microsomal antibody-1 to assess for autoimmune hepatitis
- Serum acetaminophen (paracetamol) levels
- A more detailed history of:
 - Prior and/or concurrent diseases or illness

- Exposure to environmental and/or industrial chemical agents
- Symptoms (if applicable) including right upper quadrant pain, hypersensitivity-type reactions, fatigue, nausea, vomiting and fever
- Prior and/or concurrent use of alcohol, recreational drugs and special diets
- Concomitant use of medications (including non-prescription medicines and herbal and dietary supplements), plants, and mushrooms
- Viral serologies

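### Table 11-2 requires neither a hold nor a stop for one narrow combined liver elevation when baseline AST/ALT is at or above ULN

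*Protocol*

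**What the plan says.** **Entry.** Exclusion 202 (Protocol Section 5.2) removes hepatic dysfunction "defined as aspartate aminotransferase (AST) or alanine aminotransferase (ALT) > 3 x upper limit of normal (ULN"), or bilirubin above 2x ULN. AST/ALT from ULN up to 3x ULN passes this numeric limit.

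**Permanent discontinuation (Section 11.7, Table 11-2).** Total bilirubin (TBL) above 2x ULN, or INR above 1.5 off anticoagulation, together with AST/ALT "> 3x ULN (when baseline was < ULN") and no important alternative cause.

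**Temporary withholding (same table).** Any one of the following, with no baseline condition:
- TBL above 3x ULN
- AST/ALT above 8x ULN
- AST/ALT above 5x and below 8x ULN for at least 2 weeks, or when enhanced monitoring cannot be followed
- AST/ALT "> 3x ULN with clinical signs or symptoms that are consistent with hepatitis", with jaundice among the listed examples
- ALP above 8x ULN

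INR has no withholding entry. Both columns apply only where no other cause has been identified.

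**Close observation (Section 11.7).** Required for AST/ALT above 3x ULN, or for "2-fold increases above baseline values for subjects with elevated values before drug". Tests are repeated within 24 hours. If TBL exceeds 2x ULN or INR exceeds 1.5, "retesting of liver tests, BIL (total and direct), and INR is to be performed every 24 hours until laboratory abnormalities improve". The frequency may fall once results stabilise or product is stopped in an asymptomatic subject. Other causes must be investigated.

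**Rechallenge.** "Rechallenge may be considered if an alternative cause for impaired liver tests (ALT, AST, ALP) and/or elevated TBL, is discovered", and only once the abnormalities have resolved.

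**Reporting.** The automatic 24-hour serious adverse event report covers "cases of concurrent AST or ALT and TBL and/or INR elevation, according to the criteria specified in the above". Beyond that, "Other events of hepatotoxicity and potential DILI are to be reported as serious adverse events if they meet the criteria".

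**The concern.** Liver enzyme elevation is one of the two potential risks named in Protocol Section 2.3. Elsewhere the plan allows for raised baselines. Close observation has a criterion relative to baseline, and SAP Section 9.6.2 counts AST/ALT above 3x with TBL above 2x ULN (and ALP below 2x) whatever the baseline. The permanent-discontinuation rule is the one place where a raised baseline removes the subject from the rule and nothing legible replaces it.

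At stake is the decision before the next injection. A subcutaneous dose cannot be taken back, and Section 2.1 describes a pharmacodynamic effect lasting at least 3 months. For the same on-treatment laboratory picture, a subject with a normal baseline is stopped by rule, while one with a raised baseline depends on someone deciding to stop. Reporting is affected too. If the criteria that the reporting paragraph refers back to are the table's own, baseline qualifier included, the automatic 24-hour report does not reach this case.

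**Working it through.** There is no power or alpha figure to reproduce. The check is whether the two columns of Table 11-2 cover the cases.

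**1. Reading the table.** In the extracted text the OR and AND connectors are displaced. The concurrent reading (bilirubin or INR, and AST/ALT) is supported in two ways. The reporting paragraph speaks of concurrent elevation. Also, if TBL above 2x ULN alone meant a permanent stop, withholding at above 3x ULN would be redundant.

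**2. The rules as conditions** (multiples of ULN except INR; no alternative cause):
- Withhold = TBL > 3, or AST/ALT > 8, or (5 < AST/ALT < 8 and (at least 2 weeks or monitoring not followed)), or (AST/ALT > 3 with symptoms), or ALP > 8
- Permanent = (TBL > 2, or INR > 1.5 off anticoagulation) and AST/ALT > 3 and baseline < 1

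**3. Cases** (no symptoms, ALP normal, not anticoagulated). In the first five rows the companion abnormality is TBL 2.5x, TBL 3.0x, or INR 1.8 with TBL 1.0x; all three give the same result.

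| On-treatment AST/ALT | Baseline 0.8x | Baseline 1.0x, 1.5x or 2.9x |
|---|---|---|
| 3.5x or 5x | permanent | neither |
| 6x, under 2 weeks, monitoring followed | permanent | neither |
| 6x, at least 2 weeks | withhold and permanent | withhold |
| 8x exactly | permanent | neither |
| 8.5x | withhold and permanent | withhold |
| any of these with TBL 3.5x | withhold and permanent | withhold |

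The 8x row falls between two strict inequalities and is only a boundary effect. The gap has an upper limit: higher or sustained AST/ALT, TBL above 3x, ALP above 8x, or symptoms all trigger withholding at any baseline.

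**4. One worked case.** ALT 4x with TBL 2.5x ULN (or INR 1.6):

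| Baseline | Table 11-2 now | With the withholding line below | Rise over baseline |
|---|---|---|---|
| 0.9x | permanent | permanent | 4/0.9 = 4.44 |
| 1.0x | neither | withhold | 4/1.0 = 4.0 |
| 1.5x | neither | withhold | 4/1.5 = 2.67 |
| 2.0x | neither | withhold | 4/2.0 = 2.0 |
| 2.5x | neither | withhold | 4/2.5 = 1.6 |
| 3.0x | neither | withhold | 4/3.0 = 1.33 |

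The last column shows why the choice of a baseline multiple for a permanent stop is a clinical one. At a 2-fold rule, the same ALT would be permanent up to baseline 2.0x and not at 2.5x or 3.0x.

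**5. Time to act.** Doses fall on day 1 and weeks 12, 24 and 36 (Protocol Section 4.1). Treatment-period chemistry falls at weeks 4, 12, 24, 36 and 48 (SAP Appendix A). A week 4 result leaves 12 - 4 = 8 weeks to the next dose. A week 12 or week 24 result that arrives after that day's dose leaves 24 - 12 = 12 or 36 - 24 = 12 weeks. After a week 36 result reported post-dose, or a week 48 result, no dose remains, so only the reporting question is left.

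**The case against.** The strongest objection is that the point rests on something absent from a damaged table. A row lost in extraction cannot be fully ruled out. That is why the layout check comes first. Still, the baseline qualifier itself is legible and the displaced connectors do not explain it away.

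The qualifier may also be deliberate. Section 11.7 ties its criteria to a 2009 drug-induced liver injury guidance that is not available here. A reader might infer that the table departs from that guidance; the documents cannot show it either way.

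The safeguards are substantial:
- AST/ALT above 3x ULN triggers close observation at any baseline, with 24-hourly retesting once TBL or INR is also raised.
- Liver tests are not among the blinded analytes in Section 8.2.5, so the site sees them.
- The investigator or sponsor may withdraw a subject from product (Section 7), and Section 6.2.2.1 provides for recording the reason for a withheld dose.
- The unblinded Data Review Team sees relevant laboratory results and can meet ad hoc (Section 11.3).
- Exclusions 212 and 224 let the investigator turn away clinically significant or unstable disease that passes the numeric limit.

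All of this stands and makes unnoticed re-dosing unlikely. None of it requires dosing to stop.

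On reporting, the reference back to earlier criteria can be read as the concurrent thresholds alone, in which case the report already applies. Even on the narrow reading, the case can be reported as an other medically important event under Section 11.4.

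**Conclusion.** The gap holds in the narrow form shown, with medium confidence. It needs all of the following together: baseline AST/ALT at or above ULN; AST/ALT above 3x to 5x ULN, or above 5x to 8x for under 2 weeks with monitoring followed; TBL above 2x to 3x ULN, or INR above 1.5 off anticoagulation with TBL at most 3x; ALP at most 8x; no hepatitis signs or symptoms; and no alternative cause. Its frequency cannot be derived, because the documents give neither the number of raised baselines nor an expected event count. The conclusion assumes the table reads as extracted and the concurrent interpretation in step 1.

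Three stronger inferences are tempting and not supported:
- That any combined elevation at a raised baseline escapes the rules. It does not: the 8x, sustained 5x, TBL 3x, ALP and symptom triggers apply at every baseline.
- That raised-baseline subjects, who never meet the permanent column, can drift back to dosing after a hold. The rechallenge text requires an alternative cause, so without one they have no written route back.
- That these cases would go unmonitored or unreported. Close observation is mandatory and general serious adverse event reporting remains.

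This is a cheap improvement to a written safety rule, not a threat to the trial's conclusions.

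**What to change.** Check the original layout of Table 11-2 first. If no entry for a raised baseline exists:

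(a) Add one withholding line for baseline AST/ALT at or above ULN: hold dosing when AST/ALT exceeds 3x ULN together with TBL above 2x ULN, or INR above 1.5 in a subject not on anticoagulation, and no alternative cause is identified. This closes the gap over the whole admitted baseline range. The existing rechallenge rule then governs any return to dosing.

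(b) State in the reporting paragraph that the 24-hour serious adverse event report for concurrent elevation also applies to these cases.

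Leave to the safety physicians whether some multiple of baseline should make the stop permanent.

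The cost is one table line and one cross-reference in an amendment, with no new tests. The downside is that a few more raised-baseline subjects may have a dose held. The primary estimand counts subjects regardless of product discontinuation, so they stay in the primary analysis; a held dose could take them out of the completer set used for sensitivity analysis (SAP Section 6.2).

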		
atherosclerotic cardiovascular disease in section 2.2 and 3.1 Rationale: To align with the Protocol Amendment 2
 
11. Update the descriptions of interim analysis in section 3.1 Rationale: To align with the Protocol Amendment 2
 
12. Update the descriptions of sample size in section 3.2 Rationale: To align with the Protocol Amendment 2
 
13. Update the grouping approach for region in section 4.1 Rationale: To follow the comment from TIMI and have the grouping consistent in section 4.1 and 4.2
 
14. Add a definition for reflexive approach in section 5.3 Rationale: To clarify that how to derive the variables of LDL-C and VLDL-C by using reflexive approach
 
15. Add the definition for CAS in section 6.2 Rationale: To clarify the analysis set used in sensitivity analysis
 
16. Update the descriptions of interim analysis in section 7.1 Rationale: To align with the Protocol Amendment 2
 
17. Update the wordings from “36-week” to “week 36” and from “locked” to “processed” in section 7.2 Rationale: To align with the Protocol Amendment 2
 
18. Update the wordings from “48-week” to “week 48” and from “locked” to “processed” in section 7.3 Rationale: To align with the Protocol Amendment 2
 
19. Add the approach and analysis set for sensitivity analysis in section 9.1 Rationale: To clarify what test and analysis set will be used in sensitivity analysis
 
20. Add the description for study site will be tabulated in section 9.2 Rationale: To align with the standard TFL shells, the number and percent of subjects randomized will be provided

--	--	---

21. Update section 9.2 and 9.3 to include COVID-19 impact related descriptive analysis to measure COVID impact
Rationale: To describe that the COVID-19 related PD will also be summarized and listed
22. Add a sentence for primary in section 9.5.1
Rationale: To clarify the sensitivity analysis that the primary analysis will be performed by completer analysis set as well
23. Update the wording from "treatment" to "treatment group" in section 9.5.1
Rationale: To provide more accurate wording in the description
24. Remove the sentence for log transformation in section 9.5.1
Rationale: Multiple imputation is assuming normal distribution, we are changing the sensitivity analysis from log transformation to a non-parametric method
25. Update the descriptions of additional analysis in section 9.5.1
Rationale: To provide more accurate descriptions for MCP-Mod analysis
26. Add the descriptions for following lipid parameters will be provided in section 9.5.3
Rationale: Per the suggestions from safety team, the descriptive summary for HDL-C, non-HDL-C, Triglycerides and VLDL-C will be provided as well
27. Update the MedDRA version in section 9.6.1
Rationale: Per the suggestions from safety team and to align with DMP, now the MedDRA version is 24.0
28. Update the descriptions of coding term for treatment-emergent adverse events in section 9.6.1
Rationale: Per safety team's review suggestions, TEAEs will be provided by PT only; TEAEs, serious TEAEs will be tabulated by SOC, HLT and PT; TEAEs leading to discontinuation of IP, fatal TEAEs, treatment-related TEAEs, and treatment-related serious

Amendment 2 (v2.1)	20APR2022	
TEAEs will be provided by SOC and PT
 
29. Add an adverse events of interest in section 9.6.1 Rationale: Per safety team's review suggestions, adding the "injection site reactions" as an new adverse events of interest
 
30. Update the wording in table tile in appendix C Rationale: Per the cross-functional review team's suggestions and follow up the guideline to change the wording from 'guidelines' to 'guideline'
 
Changes
 
1. Add one of the authors [REDACTED] Rationale: study statistician has been transitioned to [REDACTED]2. Update statistical analysis plan (SAP) version and date throughout this SAP Rationale: Statistical analysis plan was amended3. Edited language in Section 3.1 regarding the extended safety follow-up period. Removed the language of "Only an unblinded team will be unblinded at the end of treatment period analysis. Individuals who will remain involved in the conduct of the study will remain blinded" in Section 7.3. Rationale: to align with protocol amendment 3 that Amgen team will be unblinded after EOT analysis snapshot and extended safety follow up period will be changed to at least 24 weeks after week 48.4. Add the imputation rule for adverse event and concomitant medication partial end dates in section 8.3.2 Rationale: clarifying imputation rule for partial end dates to provide more clear instruction for programming5. Removed the wording "after week 36" in section 9.1 Rationale: EOT analysis will be performed including all visits up to week 48.
--------------------	-----------	--

9.6.4	Physical Measurements	30
9.6.5	Electrocardiogram	30
9.6.6	Antibody Formation	30
9.6.7	Exposure to Investigational Product	30
9.6.8	Exposure to Concomitant Medication	30
9.7	Other Analyses	31
9.7.1	Analyses of Pharmacokinetic or Pharmacokinetic/Pharmacodynamic Endpoints	31
10.	Changes From Protocol-specified Analyses.....	31
11.	Literature Citations / References.....	31
12.	Prioritization of Analyses.....	31
13.	Data Not Covered by This Plan.....	31
14.	Appendices.....	32
	Appendix A. Analytical Study Week Assignments	32
	Appendix B. Common Terminology Criteria for Aes (CTCAE).....	34
	Appendix C. Lipid Modifying Background Therapy.....	35

List of Abbreviations

Abbreviation	Explanation
A1C	Glycated Hemoglobin
ACC	American College of Cardiology
AE	Adverse Event
AHA	American Heart Association
ALT	Alanine Aminotransferase
ApoA1	Apolipoprotein A1
ApoB	Apolipoprotein B
AST	Aspartate Aminotransferase
AUC	Area Under the Concentration Time Curve
BID	Twice Daily
BMI	Body Mass Index
CAS	Completer Analysis Set
CK	Creatine Kinase
C _{max}	Maximum Observed Concentration
CMH	Cochran-Mantel Haenszel
CPMS	Clinical Pharmacology, Modeling and Simulation
CSR	Clinical Study Report
CTCAE	Common Terminology Criteria for Adverse Events
DIIR	Data Issue Identification and Resolution
DRT	Data Review Team
ECG	Electrocardiogram
eCRF	Electronic Case Report Form
eGFR	Estimated Glomerular Filtration Rate
EOIP	End of Investigational Product
EOS	End of Study
FAS	Full Analysis Set
HDL-C	High-Density Lipoprotein Cholesterol
hs-CRP	High Sensitivity C-Reactive Protein
hs-IL-6	High Sensitivity Interleukin 6
IARSC	Interim Analysis Review Steering Committee
ID	Identity
IP	Investigational Product
IPD	Important Protocol Deviation
IRT	Interactive Response Technology
IVRS	Interactive Voice Response System
IWRS	Interactive Web Response System

LDL-C	Low-Density Lipoprotein Cholesterol
LFT	Liver Function Test
Lp(a)	Lipoprotein(a)
LS means	Least Square Means
MCP-Mod	Multiple Comparison Procedure – Modelling
MedDRA	Medical Dictionary for Regulatory Activities
NCEP ATP III	National Cholesterol Education Panel Adult Treatment Panel III
NCT	National Clinical Trials
PK	Pharmacokinetic
PROMIS	Patient-Reported Outcomes Measurement Information System
Q12W	Every 12 Weeks
Q24W	Every 24 Weeks
QD	Once Daily
QoL	Quality of Life
QTc	Corrected QT
SAP	Statistical Analysis Plan
SC	Subcutaneous
SAS	Statistics Analysis System
UC	Ultracentrifugation
ULN	Upper Limit of Normal
VLDL-C	Very Low-Density Lipoprotein Cholesterol
vs.	Versus
WHODrug	World Health Organization Drug

1. Introduction

The purpose of this Statistical Analysis Plan (SAP) is to provide details of the statistical analyses that have been outlined within the protocol amendment 2 for study 20180109, AMG 890 Olpasiran dated 01 April 2021. The scope of this plan includes the primary analysis, the end of treatment period analysis and the final analysis that are planned and will be executed by the Amgen Global Biostatistical Science department unless otherwise specified.

2. Objectives, Endpoints and Hypotheses

